Safety and efficacy assessments	
Efficacy assessments:
 
Assessments (CT scan and bone scan) will be performed from the time of enrollment (baseline assessments) and every 12 weeks (\pm 7 working days) from the time of the first administered dose. Radiographic disease progression will be assessed using The Prostate Cancer Clinical Trials Working Group (PCWG2) modified criteria for bone disease and the Response Evaluation Criteria in Solid Tumors (RECIST criteria) version 1.1 for soft-tissue disease. Radiographic disease progression in bone will require persistence of new lesions on a confirmatory bone scan performed at least six weeks later. It is highly recommended to perform additional CT scans and bone scans if clinical progression disease is suspected.
 
During the active phase of the study treatment, each assessment will be performed in accordance with the schedule (Appendix 1: Schedule of study assessments and procedures), regardless of any delay in administration, to prevent bias in the efficacy assessment. If any of the required assessments are not performed, the disease status at that point in time will not be known.
 
Safety assessments:
 
The occurrence and maximum grade of side effects observed throughout the study will be listed and tabulated according to type and dose level. Any adverse events (AEs) that the investigator reports as unrelated to the drug will also be reported. In this study, side effects will be assessed according to the US National Cancer Institute (NCI) Common Terminology Criteria for Adverse Events (CTCAE) version 4.0.
 
Other assessments:
 
To perform the molecular analyses described in this protocol (Appendix 3: Instructions for blood sample collection. Detection of CTCs), patients will be asked to give their consent to the collection of the following biological material:
 
 - Blood samples: These will be collected at the start of the study, at the end of treatment and when documenting disease progression for the purpose of CTC.
Endpoints	
Primary endpoint:
 
The primary endpoint of this study is to assess the efficacy of radium-223 in terms of radiological rPFS.
 
Secondary endpoints:
 
Safety
 
AEs will be evaluated using the NCI-CTCAE version 4.0. Grade 3 or 4 AEs and serious adverse events (SAEs) will be assessed to determine the safety and tolerability of the various combinations of drugs.

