- Basic blood test that includes blood count, coagulation, chemistry with renal function analysis (serum creatinine, creatinine clearance according to the Cockcroft-Gault formula), liver function (AST, ALT, AF, GGT, total and direct bilirubin), glucose, sodium, potassium, calcium, chloride, magnesium, uric acid, total protein, albumin, and lactate dehydrogenase.
- PSA determination.
- HRQoL questionnaire(FACT-P, Version 04).
- Assessment of concomitant medications.
- Assessment of AEs.
- Tumor assessment: torax, abdomen, and pelvisCT scan or MRI, and bone scan prior to start of cycle every three cycles, every 12 weeks, until progression disease.
- Survival.

Blood assessment schedule for translational study:

- Blood draws prior to the start of study treatment, at the end of treatment and at the time to documented progression disease.

Biological sampling:

The first blood samples should be taken before starting study treatment (see appendix3 for more details on blood sampling procedures). The following samples should be taken at the end of treatment and at the time of disease progression.

At the time of site activation, the Sponsor will provide streck cell-free DNA BCT tubes as well as labels for the storage and transport of samples. No other tubes or labels should be used for this study. If more tubes and labels are required, these should be requested from the Sponsor in writing at least three weeks before they are required (see appendix 3).

Anamnesis and demographic data:

Anamnesis includes clinically significant diseases, surgical interventions, history of cancer (including prior antineoplastic treatments and procedures), history of smoking, alcoholism, drug addiction, as well as any medications (e.g., prescribed drugs, over-the-counter drugs, medicinal plants, homeopathic remedies, or food supplements) used by the patient in the 28 days prior to screening visit. Demographic data will include age, sex, and self-reported race/ethnicity.

Vital signs:

These will include the measurement of height (only during screening), weight, respiratory rate, heart rate, blood pressure, and body temperature. Abnormal or significant changes in vital signs from baseline should be recorded as AEs, if appropriate.

Physical Examination:

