A complete physical examination should include an examination of head, eyes, ears, nose, and throat as well as cardiovascular, dermatological, musculoskeletal, respiratory, digestive, genitourinary, and neurological systems. Changes to abnormalities identified during the baseline period should be recorded at all subsequent physical examinations. New or worsening abnormalities should be recorded as AEs, if applicable.

Physical exams should also include, as part of tumor assessment, evaluation of presence and degree of increase of lymph nodes, hepatomegaly, and splenomegaly. Limited physical exams will focus on symptoms.

Response and tumor assessments:

Tumor response will be assessed for all patients, unless they withdraw from the study for any reason not attributable to disease progression confirmed radiologically or clinically and who have not received an acceptable complete assessment of the disease. The non-measurable disease should be documented at screening and be re-assessed at every tumor assessment thereafter.

The initial assessment of tumor response will be performed at the end of cycle three. Subsequently, an efficacy follow-up will be carried out for all patients every 12 weeks ± 7 working days during the study until disease progression, the patient withdraws their consent, or death, whichever comes first. In this study, response and disease progression will be assessed using the PCWG2 guidelines for bone disease and the RECIST criteria version 1.1 for soft-tissue disease. Radiographic disease progression in bone will require persistence of new lesions on a confirmatory bone scan performed at least six weeks later. Soft-tissue progression will not require a confirmatory scan for purposes of analysis (Appendix 2: Response Evaluation Criteria in Solid Tumors Guidelines (RECIST criteria) version 1.1).

A torax, abdomen, and pelvis CT scan or MRI, and a bone scan must be performed at screening (no more than 28 days before the first trial treatment). Tumor assessments should include an assessment of all known and/or suspected sites of the disease wherever possible. Patients should have a series of selected lesions that can be assessed at each tumor assessment. The same radiographic procedure employed at screening should be used throughout the study (e.g., the use of the same contrast protocol for CT scans).

Laboratory assessments:

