- If a patient experiences grade 3 or 4 neutropenia, thrombocytopenia, or anemia lasting \leq 14 days, the administration of study drug should be delayed until recovery to grade 2 or better. A delay of up to 4 weeks is permitted.
- If a patient experiences grade 3 or 4 neutropenia, thrombocytopenia, or anemia lasting $>$ 14 days, further study drug administrations must be discontinued.
- Blood transfusion is acceptable between study drug administrations. Use of biologic response modifiers, such as G-CSF or GM-CSF, is allowed in the management of acute toxicity.

- Gastrointestinal events:

- Diarrhea. Diarrhea should be treated as per local practice. A further dose of study medication should not be given before diarrhea is recovered to no higher than CTCAE grade 2.
- Nausea/Vomiting. Nausea or vomiting should be treated as per local practice. A further dose of study medication should not be given before nausea or vomiting is recovered to no higher than CTCAE grade 2.

- Surgical intervention:

If surgery is required, the patient should continue with study treatment, if this is considered safe in the treating investigator's opinion. The surgeon needs to be notified that the patient has been given radioactive drug, and needs to follow the guidelines for radioactive protection.

- Non-pathological fractures:

For traumatic fractures in weight-bearing bones during treatment phase, the study drug administration should be delayed for two to four weeks from the time of fracture.

- Any other toxicity:

Local practice will apply. A dose delay of more than four weeks (maximum eight weeks between two injections) will lead to study drug discontinuation.

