Appendix 1: Schedule of study assessments and procedures

Study Period	Screening	Treatment period		Follow-up period		
Day	-28 to -1	Each cycle* (every 28 days)	End of treatment **	Every 3 months (Efficacy FUP) ¹²	At time of DP**	EoS (Safety FUP) ¹³
Informed Consent ¹	X					
Baseline signs/symptoms	X	X	X	X	X	
Check of inclusion/exclusion criteria	X					
Brief pain inventory (short form) (BPI-SF)	X					
Medical History ²	X					X
Physical Examination and ECOG status ^{3,4}	X	X	X	X	X	

Study Period	Screening	Treatment period		Follow-up period				
Day	-28 to -1	Each cycle* (every 28 days)	End of treatment **	Every 3 months (Efficacy FUP)¹²	At time of DP**	EoS (Safety FUP)¹³		
Concomitant Medication Reporting ⁵	X	X	X	X	X			
Health-related quality of life (HRQoL) questionnaire ⁶	X	X	X	X	X			
AE reporting ⁷	X	X	X	X	X	X		
Radiological Tumor Assessments ⁸	X	every 3 cycles	X	X	X			
Standard Laboratory Procedures								
Hematology ^{9,^}	X	X	X	X	X			
Biochemistry ^{10, ^}	X	X	X	X	X			
PSA determination [^]	X	X	X	X	X			

Study Period	Screening	Treatment period		Follow-up period			
Day	-28 to -1	Each cycle* (every 28 days)	End of treatment **	Every 3 months (Efficacy FUP) ¹²	At time of DP**	EoS (Safety FUP) ¹³	
Testosterone determination [^]	X						
Treatment Administration							
Radium-223 at dose of 55 kBq/Kg one IV injection		D1 (for a total of six IV injections)					
Research Central Laboratory Procedures							
Blood sample collection (split variant AR-V7 determination) ¹¹	X		X		X		
Blood sample collection (CTC count) ¹¹	X		X		X		

-
- * All visits must occur within \pm 7 working days from the scheduled date.
 - ** If disease progression coincides with the end of treatment visit, the evaluations planned for both visits will coincide, they will only be performed once (including blood sample for central laboratory).

 - ^ Local laboratory tests scheduled for day 1 of all cycles must be performed within 72 hours prior to confirm to the patient if treatment can be followed up.
 - 1. Signed written informed consent obtained prior to any trial-specific procedure.
 - 2. Complete medical history and demographics (including age, gender, and ethnic origin) and all medications taken the last 28 days prior to enrollment will be collected.
 - 3. Physical examination and vital signs (including respiratory rate, blood pressure measurements, heart rate, and body temperature) and weight measurement will be performed prior to enrollment.

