 - 4. ECOG performance status will be assessed before trial drug administration and before the administration of each cycle.
 - 5. Relevant concomitant medication will be recorded at screening and on an ongoing basis.
 - 6. FACT-P, Version 04
 - 7. All AEs occurring during the trial and until the treatment discontinuation visit (end of study visit) have to be recorded with grading according to NCI-CTCAE version 4.0.
 - 8. Baseline assessments of the thorax, abdomen, and pelvis (preferably CT or MRI in case of contrast allergy) must be performed no more than 28 days before the first trial treatment. Baseline bone scan must be performed no more than 28 days before the first trial treatment. Post-baseline assessments have to be performed every 12 weeks \pm 7 working days after the first dose using the same imaging method and where possible obtained at the same institution for an individual patient as used during screening until progression disease. Radiographic bone progression will require the persistence of new lesions on a confirmatory scan at least six weeks later. In those patients who receive 6 treatment cycles, the radiological tumour assessment corresponding to week 24 will be performed for the EOT visit.
 - 9. Hematological test will be performed as per local standard of care and clinical indication before treatment administration. These values should be included: hemoglobin, hematocrit, red blood cell count, platelet count, and white blood cell count with differential count (neutrophils, lymphocytes, monocytes, eosinophils, and basophils).
 - 10. Biochemistry test will be performed as per local standard of care and clinical indication before first treatment administration and first day of follow-up. These values should be included: coagulation, chemistry with renal function analysis (serum creatinine, creatinine clearance according to the Cockcroft-Gault formula), liver function (AST, ALT, ALP, direct and total bilirubin), glucose, sodium, potassium, calcium, chloride, magnesium, uric acid, total protein, albumin, and lactate dehydrogenase.
 - 11. Blood sample for central laboratory prior to the start of study treatment, at the end of treatment and at time to documented progression disease (if the patient ends treatment due to progressive disease, only one blood sample will be sent at this point).

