Approximate duration of subject participation	Patients will be treated with radium-223 at four-week intervals for six intravenous injections.  Patients who complete the study treatment during its active treatment phase will enter a follow-up period with radiological tumor assessment every three months (±7 days) from the last dose of study treatment until documented disease progression.
Calendar and estimated completion dates	Start Recruitment (FPI): Nov-2016 End of Recruitment (LPI): Oct-2018 Follow-up period for progression: Sep-2019 Follow-up extension for safety: Apr-2021 Final report: Mar-2018 Final safety report: Aug-2021

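### Tumour scans run on two clocks, weeks from first dose and treatment cycles, which separate when a dose is delayed; a site following the cycle wording can scan late and, on average, lengthen recorded PFS.

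*Protocol*

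**What the plan says.** **Calendar clock.** The protocol synopsis (efficacy assessments) sets CT and bone scans every 12 weeks, ±7 working days, counted "from the time of the first administered dose". It adds that assessments in the treatment phase follow Appendix 1 "regardless of any delay in administration, to prevent bias in the efficacy assessment". Note 8 of Appendix 1, attached to the tumour-assessment row, agrees: "Post-baseline assessments have to be performed every 12 weeks", with the same window, after the first dose. The SAP deviation table (section 6.1) also checks scans against 12 weeks and grades a late one as minor.

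**Cycle clock.** Section 5.2 of the protocol states "The initial assessment of tumor response will be performed at the end of cycle three", with no week number. It places full visits on day 1 of every third cycle and lists CT or MRI and "bone scan prior to start of cycle every three cycles, every 12 weeks, until progression disease". The treatment-period cell of the Appendix 1 grid reads "every 3 cycles".

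**What separates them.** Section 5.2 makes a cycle 28 days only in the absence of delay. Section 6.11 permits a delay of up to 4 weeks for myelosuppression, and for other toxicity says: "A dose delay of more than four weeks (maximum eight weeks between two injections) will lead to study drug discontinuation".

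**Follow-up.** The protocol (synopsis, 3.2, 5.3 and Appendix 1 note 12) asks for scans every three months after treatment without naming the date from which the months are counted. The SAP synopsis counts them "from the last dose of study treatment until documented disease progression".

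**The concern.** Progression found on imaging is dated by the scan that shows it, so the scan schedule is part of how the primary endpoint is measured. If a late dose also makes the scan late, recorded PFS depends on dosing history as well as on disease. The trial has no control arm in which the same shift could cancel. Recorded times are compared with a fixed 3-month null, and the average shift favours a positive result.

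The sponsor recognised this bias and wrote a rule against it. But the rule stands only in the synopsis. Section 5.2 does not repeat it, and the Appendix 1 grid to which the synopsis refers has a cell and a note that disagree once a dose is delayed. The censoring rules for missed visits (protocol Table 2; SAP 8.5 and Appendix I) also need a single grid to define when an assessment was missed.

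**Working it through.** **1. The plan's own figures.** Three cycles × 28 days = 84 days = 12 weeks, so the two clocks agree exactly when nothing is delayed. The sample size also reproduces. Inputs from protocol 8.2 are medians of 3 and 6.3 months, one-sided alpha 0.05, 80% power, 23 months of accrual and 11 of follow-up.
- Events = ((1.645 + 0.842)/ln(6.3/3))² = 11.23.
- The probability of an event under the target is 0.892, so n = 11.23/0.892 = 12.6, rounded up to 13.
- 13/0.25 = 52.

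Scan timing does not enter this calculation, so reconciling the clocks leaves N at 52.

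**2. First scan under each clock** (30.4375 days per month).

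| Dosing before injection 4 | Calendar clock | Cycle clock |
|---|---|---|
| No delay | week 12 (2.76 months) | week 12 (2.76 months) |
| One 4-week delay | week 12 | week 16 (3.68 months) |
| All three intervals at 8 weeks (ceiling) | week 12 | week 24 (5.52 months) |

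The window of 7 working days is 7/5 = 1.4 weeks, so it cannot absorb a 4-week difference.

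**3. Mean recorded PFS.** Assume exponential PFS with hazard λ = ln 2/median, events found only at scans, first scan at time f, and later scans every D = 2.76 months. Then

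mean = f + D·exp(−λf)/(1 − exp(−λD)).

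- Median 3, f = 2.76: 2.76 + 2.76 × 0.5285/0.4715 = 5.85 months.
- Median 3, f = 3.68: 3.68 + 2.76 × 0.4273/0.4715 = 6.18 months. Difference: 0.33 month.
- Median 6.3, f = 2.76: 2.76 + 2.76 × 0.7381/0.2619 = 10.54 months.
- Median 6.3, f = 3.68: 3.68 + 2.76 × 0.6671/0.2619 = 10.71 months. Difference: 0.17 month.

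These differences apply if every patient has one 4-week delay. Simulated means agree: 5.86 and 6.18 months at a median of 3; 10.53 and 10.71 at 6.3.

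**4. Effect on the test.** The SAP (7.1.1) uses an exponential maximum-likelihood test. With O events and E = λ₀ × total recorded time, where λ₀ = ln 2/3, it is positive when √O·ln(E/O) > 1.645. Simulation at n = 52, a true median of 3 months and the planned accrual and follow-up gave:

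| Patients with one 4-week delay | Mean estimated median (months) | Positive rate |
|---|---|---|
| 0% | 4.08 | 0.756 |
| 10% | 4.10 | 0.778 |
| 20% | 4.13 | 0.794 |
| 30% | 4.16 | 0.821 |
| 100% | 4.32 | 0.917 |

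From no delay to 10–30% delayed, the increase is 0.022 to 0.065, or about 2 to 7 percentage points. A second run gave 0.74, 0.77, 0.78, 0.81 and 0.92, so the last digit is simulation noise. The one-sample log-rank test named in the protocol gave almost identical rates.

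**5. The recorded median.** At a true median of 3 months it is 5.52 months on the 12-week grid, but 3.68 months if every first scan is at week 16. The later first scan falls after the true median, so more than half of patients are dated there.

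**6. Follow-up anchor.** Without delay, injection 6 falls at week 20. Three months later is about week 20 + 13 = 33, against week 36 on the first-dose grid.

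**The case against.** The strongest reply is that the calendar rule already governs. Note 8 sits on the very row that counts in cycles, and it calls the second scan week 24. Section 5.2 adds a 12-week gloss to its full-visit and scan entries. The sentence after the one on the first scan gives a 12-week interval, and the SAP would flag a scan taken four weeks late. This stands in part: postponement is a risk at a site that follows the cycle wording, not a certain result. It does not remove the conflict, because the gloss is true only without delay and the first-scan sentence carries no gloss.

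A reader might also infer more than the documents support:

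- **That each delayed patient gains 0.92 month (4 weeks), 31% of the null.** This holds for a patient who progresses before week 12. One who progresses in weeks 12–16 is recorded at week 16 instead of week 24, which is 1.84 months shorter. The net mean shift at the null is about 0.33 month.
- **That a first scan at week 24 is realistic.** It needs all three intervals at the permitted maximum. Section 6.11 stops study drug for grade 3–4 cytopenia lasting more than 14 days, which makes this remote by that route.
- **That the sickest patients are the ones scanned late.** Section 6.11 does list progression and cytopenia among reasons for delay. But documented progression is already an event, the synopsis strongly recommends extra scans when progression is suspected, and deaths and symptomatic skeletal events count on their own dates.
- **That the SAP's last-dose anchor also inflates PFS.** The follow-up scan then comes earlier (about week 33 against week 36), so this is an inconsistency with no upward bias shown.

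**Conclusion.** The inconsistency is real and worth correcting. The synopsis and note 8 say one thing, the cycle wording in section 5.2 and the Appendix 1 grid says another once a dose is delayed, and a permitted delay exceeds the visit window. Followed literally, the cycle wording moves the primary test towards a positive result by about 2 to 7 points at the null with 10–30% of patients delayed.

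That size is modest beside the bias from the 12-week interval itself, which already gives a positive rate of about 0.76 at a true median of 3 months with no delay and which this correction leaves in place. The documents do not support a claim that dose delay always postpones the scan, or that it lengthens the reported median.

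The figures assume exponential PFS, one 4-week delay before the first scan, scans every 12 weeks after it, and no event found between scans. The share of patients delayed is also assumed. Deaths, skeletal events and unscheduled scans would shrink the effect.

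**What to change.** In protocol section 5.2 (full visits, tumour-assessment entry and first-scan sentence) and in the treatment-period cell of the Appendix 1 grid, replace the cycle wording for tumour scans with weeks 12, 24, 36 and so on from first dose, ±7 working days, irrespective of dose delay. This is the rule the synopsis and note 8 already state. Give the three-monthly follow-up scans the same first-dose anchor in the synopsis, sections 3.2 and 5.3 and Appendix 1 note 12, and reconcile the SAP synopsis with it.

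The cost is an edit in each of these places. A delayed patient's scan may no longer coincide with an injection visit. The stated 12-week schedule gains no scans during treatment, and sample size and dosing are unaffected.

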5.3. Follow-up phase

Patients who complete the study treatment during its active treatment phase will enter a follow-up period with radiological tumor assessment every three months (± 7 working days) until documented disease progression and safety evaluation during 2 years from the last dose of study treatment. If patient discontinued treatment for any other reason than progression, tumor reevaluation will be included in the assessment.

- Assessment schedule after progression or at the end of treatment for any other reason: After progression or at the end of treatment for any other reason the following assessments will be performed within a period of 28 days (if end of treatment is not confirmed in some of the scheduled full visits):
 - Assessment of symptoms.

- Physical examination and measurement of weight, vital signs, and ECOG performance status.
- Basic blood test that includes blood count, coagulation, chemistry with renal function analysis (serum creatinine, creatinine clearance according to the Cockcroft-Gault formula), liver function (AST, ALT, ALP, GGT, direct and total bilirubin), glucose, sodium, potassium, calcium, chloride, magnesium, uric acid, total protein, albumin, and lactate dehydrogenase.
- PSA determination.
- HRQoL questionnaire(FACT-P, Version 04).
- Assessment of concomitant medications.
- Assessment of AEs.
- Tumor assessment: torax, abdomen, and pelvisCT scan or MRI, and bone scan.
- Blood sample for translational study, which is then sent to central laboratory.
- Survival.

After disease progression, a safety follow-up visit will be performed within three following months and 2 years after last dose of study treatment (including survival status and post-study anticancer therapy evaluation). Safety evaluation after progression will include follow-up of symptomatic skeletal related events and overall survival. Contact by telephone is permitted.

In addition, any events \geq grade 2 will be followed until improvement to baseline levels is observed, complete recovery or resolution to grade 1, consent is withdrawn by the patient, patient death, or until follow-up is no longer possible.

